### General Physical Examination Findings

At screening for inclusion into the study, any clinically significant abnormality should be recorded as a preexisting condition and reported on the Demographics eCRF. From the time of consent

forward, any new clinically significant findings or abnormalities that meet the definition of a protocol defined AE must also be recorded and documented as an AE.

#### Adverse Event Reporting Period

The study period during which AEs must be reported is normally defined as the period from the initiation of any study procedures to the end of the study treatment follow-up. The start of study procedures is considered to be the point of consent. Any AEs which fit the protocol defined reportable events must be reported from the time of consent until study completion.

At each contact with the subject the investigator must seek information on AEs by specific questioning and, as appropriate, by examination. Information on protocol defined AEs should be recorded immediately in the source document and also in the appropriate AE module of the eCRF. All clearly related signs, symptoms and abnormal diagnostic procedure results should be recorded in the source document and grouped under one diagnosis as appropriate. The clinical course of each event should be followed until resolution or until it is determined at the end of the study that the AE will not resolve.

#### 8.2 General Adverse Event Definitions

Following is a list of general AE definitions. For the purposes of this study, only SAEs, excluding elective procedures, as well as all AEs related to the operative site should be reported.

#### Adverse Event

An **AE** is any untoward medical occurrence in a clinical investigation subject, which changes the medical baseline of the subject. An AE can be an unfavorable and unintended sign, symptom or disease, whether or not related to the study device (AEs may also be referred to as complications). See Section 8.1, Reporting of Adverse Events, for the AE reporting requirements for this study.

### Anticipated Adverse Event

An **anticipated AE** is an AE, of which the nature, severity or degree of incidence is known and identified in applicable product labeling, published literature or study protocol. The list of anticipated events is provided in Section 12, Risk/Benefit Assessment.

#### Serious Adverse Event

A **SAE** meets one or more of the following definitions:

- Resulted in in-patient hospitalization
- Resulted in prolonged existing hospitalization
- Resulted in persistent or significant disability/incapacity
- Resulted in permanent impairment of a body function or permanent damage to a body structure
- Necessitated medical or surgical intervention to preclude permanent impairment of a body function or permanent damage to a body structure
- Was a life-threatening situation
- Resulted in patient death

Elective procedures meeting the definition of an SAE do not need to be reported as AEs according to this study protocol.

#### Adverse Device Effect

An **adverse device effect** (ADE) is a negative change in the subject's health that may have been caused by, or associated with, the use of the device.

#### Unanticipated Adverse Device Effect

An **unanticipated adverse device effect** (UADE) is any serious adverse effect on health, safety or any life-threatening problem or death caused by, or associated with, a device if that effect is a problem or death not previously identified in nature, severity or degree of incidence, or any other unanticipated serious problem associated with a device and related to the rights, safety or welfare of subjects.

### 8.3 Study Sponsor Notification by Investigator

Of reportable AEs, certain events must be submitted to Stryker within 24 hours for timely notification:

#### Adverse events that require time sensitive reporting:

An adverse event should be reported to the study sponsor (CSM or CSA) either by telephone/fax/email within 24 hours of the site's becoming aware of the event if any of the following apply:

- The AE is considered by the investigator to be device related or if the investigator is uncertain regarding the device related assessment;
- The AE required a reoperation of the study hip or a revision of any study hip components.

An AE eCRF must be completed by the investigator within 24 hours. If a SAE occurs, the de-identified source documentation must be uploaded to the Subject Binder of Stryker's Electronic Data Capture (EDC) system, within 24 hours of the investigative center's SAE awareness. See Section 11, Data Management, for additional details of Stryker's EDC system. These reports will be evaluated by Stryker to determine if a PER is required.

It is recommended that all other reportable adverse events are reported on eCRFs and submitted to Stryker within 2 weeks.

At the time of the initial report, the following information should be provided:

- Subject number
- A description of the event
- Date of onset
- Current status

- Whether study treatment was discontinued
- Investigator assessment of the association between the event and the study treatment

# 8.3.1 Ethics Committee/Institutional Review Board Notification by Investigator

Reports of AEs (including follow-up information) must be submitted to the Ethics Committee (EC) or Institutional Review Board (IRB) according to their specific requirements. Copies of each report and documentation of EC/IRB notification and receipt will be kept with the investigator's study files.

### 8.4 Recording of Adverse Events

All protocol defined AEs occurring during the study period must be recorded; this includes events that occur between visit intervals. The clinical course of each event should be followed until resolution or stabilization.

### 8.5 Medical Monitoring

It is the responsibility of the investigator to oversee the safety of the study at his/her center. This safety monitoring will include careful assessment and appropriate reporting of AEs, as previously noted. Stryker will conduct formal investigations via the Product Surveillance Department of those AEs which are submitted through our PER System.

# 9 Statistical Plan

### 9.1 Efficacy

### 9.1.1 Primary Efficacy Parameters

The primary efficacy parameter is acetabular component revision for any reason.

### 9.1.2 Secondary Efficacy Parameters

The secondary efficacy parameters include:

- The usage of screw fixation
- HHS at the 1-, 3- and 5-year follow-up visits
- SF-12 scores at the 1-, 3- and 5-year follow-up visits
- LEAS at the 1-, 3- and 5-year follow-up visits
- EQ-5D at the 1-, 2-, 3-, 4- and 5-year follow-up visits
- Follow-Up Questionnaire annually in postoperative years 6-10

### 9.1.3 Primary Efficacy Hypothesis

The null hypothesis,  $H_0$ , is that the success rate at 5 years postoperative is less than  $\delta$ . The alternative hypothesis,  $H_a$ , is that the success rate at 5 years postoperative is greater than or equal to  $\delta$ . When  $\delta$  = 94%, the hypothesis is a test for non-inferiority. When  $\delta$ =99%, the hypothesis is a test for superiority.

 $H_0$ :  $p < \delta$ 

 $H_a: p \ge \delta$ 

### 9.1.4 Primary Efficacy Analysis

A case success is defined as no incidence of revision or removal of the acetabular component within 5 years. A 90% confidence interval of the success rate will be computed at 5 years postoperative. If the lower bound of this confidence interval is greater than 94%, the non-inferiority hypothesis will be supported. If the lower bound of this confidence interval is above 99%, the superiority hypothesis will be supported. The Kaplan-Meier survival curve of revision or removal of the acetabular component will also be displayed using SAS/PROC LIFETEST.

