### **Study Synopsis**

Title	A prospective, post-market, multi-center study of the Tritanium® Acetabular Shell
Short Title	Tritanium ® Primary Acetabular Shell Study
Protocol Number	69
Phase	Post-market

	This study will be a prospective, non-randomized evaluation of					
	the Tritanium ® Acetabular Shell for primary total hip					
	replacement (THR) with a cementless application in a					
	consecutive series of patients who meet the eligibility criteria.					
	Half of the cases will use the X3 ® polyethylene insert alone as					
	the bearing surface; the other half will use the MDM™ liner					
	coupled with a compatible ADM/MDM ™ X3 ® insert as the					
	bearing surface. Cases receiving the MDM™ liner may be					
	coupled with Stryker 22.2 mm or 28 mm LFIT ™ CoCr, BIOLOX					
	delta or alumina ceramic heads. All cases will be implanted					
	with a compatible Stryker femoral stem.					
	Data from the Trident® X3® Polyethylene Insert Study will be					
	used as a historical control for secondary objectives. This study					
Methodology	was chosen for the following reasons:					
	Similar indication (primary THR)					
	The acetabular shell (Trident® HA Hemispherical					
	Acetabular Shell) used in this study is a predicate for the					
	Tritanium ® Acetabular Shell, with similar design					
	features.					
	The follow-up intervals and data collected in the Trident®					
	X3 ® Study closely match the design of the current study.					
	The survivorship value used for development of the statistical					
	plan was calculated as a mean of the mid-term results					
	published for three studies of similar acetabular shells. Articles					
	presenting long-term results of additional acetabular shells of					
	similar design will be used for comparison at the end of the					
	study as available.					
	Follow-up of each primary THR case to 10 years					
Study Duration	Enrollment period of 18-24 months					
	Approximate 13-year total duration					
Study Center(s)	7 – 12 centers					
· · · · · · · · · · · · · · · · · · ·	1					

Hypothesis	The success rate, defined as freedom from acetabular revision, for hips implanted with the Tritanium® Acetabular Shell, is no worse than for hips implanted with similar technology as reported in the literature and Trident® X3® Study historical control at 5 years postoperative.					

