#### Primary:

The 90% confidence interval of the success rate will be computed at 5 years postoperative. For the non-inferiority comparison, the lower bound of this 90% confidence interval will be compared with 94%. For the superiority comparison, the lower bound of this 90% confidence interval will be compared with 99%.

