#### 7.4 Annual Follow-up Visits

Clinical data will be collected via office visit by the investigator at the following annual postoperative intervals: 1-year, 3-year and 5-year. Tools for postoperative evaluation will be the HHS, AP hip, AP pelvis and lateral radiographs.

Patient outcomes data will also be collected via patient questionnaires. At each of the 1-year, 3-year and 5-year follow-up visits, the SF-12, LEAS and EQ-5D are required. These same questionnaires are also required at 2-year and 4-year intervals, and may be completed during an office visit or sent to the subject to be completed, initialed and dated and returned to the investigative site.

All clinical data, radiographs, and patient outcomes data must be collected within  $\pm$  2 months of the 1-year and 2-year anniversary dates. For remaining annual time points, the window expands to  $\pm$  3 months of the 3-year anniversary date and  $\pm$  4 months of the 4-year and 5-year anniversary dates.

The initial phase of the study will continue for 5 years after surgery and include collection of the previously described radiographs, HHS, and SF-12, LEAS and EQ-5D patient questionnaires. In the second phase of the study, all subjects will complete a brief satisfaction questionnaire annually at the 6-year, 7-year, 8-year, 9-year and 10-year follow-up intervals. This form may be completed by the SC during a patient telephone interview, or by the patient either at home or during a clinic visit. The questionnaire will be used to obtain the following information, at a minimum:

- Patient satisfaction with the hip replacement
- Presence of any pain in the study hip
- Any surgeries performed on the study hip

The questionnaire will also provide information on any revisions and enable calculation of the Kaplan-Meier survival curve necessary to meet the primary endpoint of the study.

Additionally, at investigational sites that choose to continue collecting clinical and radiographic data during the second phase of the study, subjects will be evaluated again at 7 and 10 years after surgery.

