#### 9.4.2 Sample Size Calculation

A literature review shows that at 5 years of follow-up there is a 97.9% to 99.6% success rate in similar devices using revision or removal of the acetabular component as the defining factor. Based on these results, it should be a reasonable assumption that the base success rate of revision or removal of the Tritanium® Acetabular Shell will be approximately 99% at 5 years. Using a base success rate of 99% from the literature and a delta of 5%, it was calculated that 142 total cases implanted with the Tritanium® Acetabular Shell would be needed to prove non-inferiority with 95% power. With a minimum of 142 cases analyzed, the primary hypothesis of the study will be met if the lower bound of the 90% confidence interval for the 5-year success rate is greater than 94%. By factoring in a 20% lost to follow-up rate within a 5-year period, the required sample size increases to 177 cases. Cases will continue to be enrolled until a total of 240 cases are implanted with the Tritanium® Acetabular Shell; half of these cases will use the X3® polyethylene insert alone as the bearing surface and the other half will use the MDM™ liner coupled with a compatible ADM/MDM™ X3® insert as the bearing surface.

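### The superiority rule (lower 90% limit above 99%) cannot be met with 240 or fewer cases under a Clopper-Pearson or Wilson interval, even with no revisions; intervals that can pass do so only at zero revisions, with one-sided error above 5% near 99%

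*Combined protocol and SAP*

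**What the plan says.** The superiority comparison appears three times.

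- Synopsis, Statistical Methodology (Primary): "For the superiority comparison, the lower bound of this 90% confidence interval will be compared with 99" percent.
- Section 9.1.3: with the threshold δ set to 99%, "the hypothesis is a test for superiority".
- Section 9.1.4: "If the lower bound of this confidence interval is above 99%, the superiority hypothesis will be supported".

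None of these names the method for the interval. Section 9.1.4 adds that "The Kaplan-Meier survival curve of revision or removal of the acetabular component will also be displayed using SAS/PROC LIFETEST", and Section 7.4 says the later questionnaires will "enable calculation of the Kaplan-Meier survival curve necessary to meet the primary endpoint of the study".

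Section 9.4.2 gives the basis for the sample size. From the literature, "there is a 97.9% to 99.6% success rate in similar devices". The calculation then proceeds "Using a base success rate of 99% from the literature and a delta of 5" percent, which gives 142 analysed cases for non-inferiority at 95% power and 177 after a 20% loss. Enrolment continues to 240 implanted cases. No power is given for superiority. Section 9.4.4.1 bases the primary analysis on a per-protocol population that leaves out cases unavailable at 5 years.

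The synopsis hypothesis is one of non-inferiority only: the success rate "is no worse than for hips implanted with similar technology as reported in the literature" and in the historical control.

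**The concern.** A 99% threshold leaves almost no room for an interval below an observed rate of 100%. If the largest possible sample with a perfect result still gives a lower limit under 99%, the rule cannot be satisfied by any data. If another interval method does satisfy it, the conclusion depends on a choice that the plan leaves open.

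The threshold also equals the success rate that the plan assumes to be true. On that assumption a valid one-sided 5% test passes at most 5% of the time.

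At stake is a superiority claim written into the primary hypothesis and primary analysis. With no revisions, an analyst could report superiority or its absence from the same data, and neither report would contradict the plan.

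**Working it through.** **Inputs.** Threshold 99% and 90% interval (Section 9.1.4). Maximum 240 cases, 20% loss, assumed rate 99%, literature range 97.9% to 99.6% (Section 9.4.2). Analysed cases after loss: 240 × 0.80 = 192. The interval is read as two-sided, with 5% in the lower tail and z = 1.645.

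**The plan's own figure.** One-sample binomial test, p0 = 0.94, p1 = 0.99, difference d = 0.05, one-sided 5%, power 95%:

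- n = [1.645·√(0.94·0.06) + 1.645·√(0.99·0.01)]² / 0.05² = 122.9
- with continuity correction, (n/4)·[1 + √(1 + 2/(n·d))]² = 142.2, which matches the stated 142.

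The same formula at one-sided 10% gives 106.7, so 5% per tail is the plan's own calibration. For the loss, 142/0.8 = 177.5, stated as 177.

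**Lower limit with zero revisions**

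| Method | Formula at zero revisions | n = 240 | n = 192 | Smallest n that passes |
|---|---|---|---|---|
| Clopper-Pearson | 0.05^(1/n) | 98.76% | 98.45% | 299 |
| Wilson | n/(n + 1.645²) | 98.89% | 98.61% | 268 |
| Mid-P | 0.10^(1/n) | 99.05% | 98.81% | 230 |
| Jeffreys | 5% point of Beta(n + 0.5, 0.5) | 99.20% | 99.01% | 191 |
| Wald; Kaplan-Meier with Greenwood variance (plain or log scale) | estimate 1, variance 0 | 100% | 100% | any |

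The log-log Kaplan-Meier interval is undefined at zero revisions.

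**Lower limit with one revision, n = 240**

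- Wald or plain Greenwood, no losses before the revision: 239/240 − 1.645·√[(239/240)(1/240)/240] = 98.90%. Greenwood on the log scale is also 98.90%.
- Jeffreys 98.38%, mid-P 98.30%, Wilson 98.15%, Clopper-Pearson 98.04%, Greenwood log-log 97.86%.

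All fail. Wald would need 265 cases to pass with one revision and Clopper-Pearson 473. The Kaplan-Meier references in Sections 7.4 and 9.1.4 therefore do not rescue the rule: that route passes only when its variance estimate is zero.

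**Error of a rule that passes only at zero revisions.** The chance of a pass is pⁿ at true rate p.

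| True rate | n = 240 | n = 192 | Meaning |
|---|---|---|---|
| approaching 99% | 0.99²⁴⁰ = 9.0% | 0.99¹⁹² = 14.5% | error, nominal 5% |
| 98% | 0.98²⁴⁰ = 0.8% | 0.98¹⁹² = 2.1% | error |
| 99.6% | 0.996²⁴⁰ = 38.2% | 0.996¹⁹² = 46.3% | best possible power |

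Setting pⁿ = 0.05 gives p = 98.76% (n = 240) and 98.45% (n = 192). The error exceeds 5% only between those rates and 99%.

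**Size needed for a valid test.** A Clopper-Pearson test against 99% first reaches 80% power at a true 99.6% with 1,182 cases (at most 6 revisions, power 80.1%).

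**The case against.** The strongest reply is that superiority is incidental. The synopsis hypothesis and the sample size concern non-inferiority, and Section 9.4.2 ties success on the primary hypothesis to the 94% limit alone. An unpowered superiority look after non-inferiority is not in itself an error. This stands as a limit on the weight of the point: the main conclusion of the study is untouched. It does not remove the point, because Sections 9.1.3 and 9.1.4 place the 99% test inside the primary hypothesis and analysis.

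A second reply is that the rule is not strictly unattainable, since the plan does not prescribe Clopper-Pearson or Wilson. That is correct, and the claim should not be shortened to say that it is. The intervals that pass do so only at zero revisions, and near 99% their error is above nominal. The excess is confined to a narrow band of true rates.

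A third reply is that the text could mean a one-sided 90% bound. Zero revisions would then pass from 230 cases (Clopper-Pearson) or 163 (Wilson). The text does not say this, the stated 142 does not reproduce at one-sided 10%, and at 240 or fewer cases the error at 99% would still be 9.0% or more.

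Finally, the power ceiling of about 46% applies to 192 to 240 analysed cases. At the plan's minimum of 142, Wald would pass with probability 0.996¹⁴² = 56.6% at a true 99.6%, but its error near 99% would be 0.99¹⁴² = 24.0%.

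**Conclusion.** The concern holds. Under a two-sided 90% interval, the superiority rule fails for every possible result at 240 or fewer cases with Clopper-Pearson or Wilson. Where another interval allows a pass, it needs exactly zero revisions. At the plan's assumed 99% that event has a 9.0% (240 cases) to 14.5% (192 cases) chance, which is also the one-sided error at the threshold. With one or more revisions superiority fails under every method tried; with none, the unnamed interval method decides.

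This rests on three assumptions: 5% in the lower tail, which the plan's own 142 supports; a binary outcome per analysed case; and 192 to 240 cases analysed. The change should be made, but the defect is confined to the superiority comparison. The 94% rule works: at 240 cases Clopper-Pearson allows up to 8 revisions, with exact error 4.6% and power 99.9% at a true 99%.

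**What to change.** Delete the 99% comparison in all three places.

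1. Synopsis, Statistical Methodology (Primary): remove the sentence that compares the lower bound with 99%.
2. Section 9.1.3: remove the sentence that defines δ = 99% as superiority, leaving δ = 94%.
3. Section 9.1.4: replace the superiority sentence with: *No superiority claim will be made. Beyond the 94% test, the 5-year success rate and its 90% confidence interval will be reported descriptively.*

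The cost is three wording changes and no new data. The sponsor gives up a claim that the design cannot validly support.

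Separate and optional: name the Clopper-Pearson interval in Section 9.1.4 for the 94% decision. Its exact error at a true 94% is 2.6%, 2.4% and 4.6% at 142, 192 and 240 cases, against 6.8%, 10.5% and 8.5% for Wald. Wilson has the same cut-offs as Clopper-Pearson at 142 and 240, and 5.4% error at 192. The cost of Clopper-Pearson is power of 94.5% instead of the stated 95% at 142 analysed cases; at 192 or 240 it is at least 98.7%.

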### 9.1.5 Secondary Efficacy Analysis

A two-sided 0.05 alpha level will be used.

For comparison of usage of bone screw fixation between the Tritanium® Primary Acetabular Shell Study and the Trident® X3® Polyethylene Insert Study, a Chi-square test or Fisher's exact test will be used. If there are any statistically significant differences in baseline variables (e.g. age, gender, diagnosis) between the groups, they will be addressed as covariates and ANOVA or ANCOVA will be used.

For comparison of HHS, and SF-12 and LEAS at 1, 3 and 5 years postoperative between the Tritanium® Acetabular Shell and Trident® X3® Polyethylene Insert studies, a t-test or Wilcoxon test will be used. If there are any statistically significant differences in baseline variables (e.g. age, gender, diagnosis) between the groups, they will be addressed as covariates and ANOVA or ANCOVA will be used.

EQ-5D values and changes from baseline will be presented for each interval. Data from the Follow-Up Questionnaire will be used as an input to the Kaplan-Meier survival curve for postoperative years 6-10; any adverse events collected via the Follow-Up

Questionnaire will be reported on a separate Adverse Event eCRF and included in the safety analysis.

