	Primary:  To demonstrate, through absence of revision at 5 years postoperative, that acetabular replacement with the Tritanium® Acetabular Shell provides clinical results comparable to similar acetabular components.  Secondary:  • To study rates of screw fixation usage in Tritanium®					
	Acetabular Shell (cluster hole) procedures and compare with those reported in the Trident® X3® Polyethylene Insert Study.					
Objectives	To compare pain, function and health related quality of life (QOL) between the Tritanium® Acetabular Shell combined group and the above-referenced historical control group. The following outcomes measures will be used for this comparison:					
	
 
Harris Hip Score (HHS)
 
Short Form-12 (SF-12)
 
Lower Extremity Activity Scale (LEAS)
 
EQ-5D
 
					
	1-year, 3-year, and 5-year HHS, SF-12 and LEAS data will be compared to the historical control with respect to improvement from preoperative scores. The EQ-5D data will be summarized and presented.					

	An additional Follow-Up Questionnaire will be
	administered annually in postoperative years 6-10 to
	assess patient satisfaction and pain, and to capture
	adverse events. This questionnaire will provide the
	survivorship information necessary to evaluate the
	primary objective of the study.
Objectives	To review radiographic stability and complications
	between those hips implanted with the Tritanium®
	Acetabular Shell and those in the historical control
	group.
	Published complication rates with similar devices, as
	well as complications related to cementless acetabular
	replacement, will be reviewed.
	Cases will be enrolled until 240 cases have received the Tritanium® Acetabular Shell
Number of Subjects	
 
Treatment 1: 120 cases with X3® polyethylene insert
 
Treatment 2: 120 cases with MDM™ liner and ADM/MDM™ X3® insert
 

	Inclusions:
	A. Patient has signed an IRB approved, study specific
	Informed Patient Consent Form.
	B. Patient is a male or non-pregnant female age 18 years
	or older at time of study device implantation.
Diagnosis and Main	C. Patient has primary diagnosis of Non-Inflammatory
Inclusion/Exclusion Criteria	Degenerative Joint Disease (NIDJD).
	D. Patient is a candidate for a primary cementless total hip
	replacement.
	E. Patient is willing and able to comply with postoperative
	scheduled clinical and radiographic evaluations and
	rehabilitation.

	Exclusions:

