#### Secondary:

### A Fisher's exact test or Chi-square test will be used to compare the usage of screw fixation between the Tritanium® Acetabular Shell and Trident® X3® Polyethylene Insert studies. If there are any statistically significant differences in baseline variables (e.g. age, gender, diagnosis) between the groups, they will be addressed as covariates and ANOVA or ANCOVA will be used.

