#### 1.4 Clinical Data to Date

Solid back and cluster hole versions of the Tritanium® Acetabular Shell are currently available in the United States. This study is the first prospective data collection on both versions of the device.

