#### 2.1.2 Secondary

Usage of bone screw fixation will be recorded and compared between the Tritanium® Acetabular Shell group and the Trident® HA Hemispherical Shell group (Trident® X3® Polyethylene Insert Study).

Additionally, pain, function and health-related QOL data for the Tritanium® Acetabular Shell group will be collected at postoperative time points and compared with the subjects' preoperative status, as well as with the historical control group and with published literature for similar highly porous acetabular shells. It is expected that the HHS, SF-12 and LEAS outcomes in the study group will be comparable to the historical control. It is expected that the EQ-5D outcomes in the study group will be comparable to published results for similar devices.

Lastly, radiographic stability and complications between those implanted with the Tritanium® Acetabular Shell and the historical control group will be reviewed.

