#### Tritanium® Acetabular Shell:

The catalog numbers for the Tritanium® Acetabular Shell permissible according to this study protocol will be in the following format, where 'XXX' varies by size:

500-03-XXX (solid back) 502-03-XXX (cluster hole)

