#### Acetabular Bone Screws

HOWMEDICA OSTEONICS 6.5mm Bone Screws can be used with the dome screw holes of the acetabular shells.

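### The screw-usage objective is limited to cluster-hole procedures, but the planned test is not, and it drops cases unavailable at 5 years from an outcome known at surgery

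*Combined protocol and SAP*

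**What the plan says.** **Population for screw usage**

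- Study Synopsis, Objectives: screw fixation rates in Tritanium "Acetabular Shell (cluster hole) procedures and compare with those reported in" the Trident X3 Polyethylene Insert Study. This is the only place that carries the cluster-hole limit.
- Study Synopsis, Statistical Methodology: a Fisher's exact or chi-square test to "compare the usage of screw fixation between the Tritanium® Acetabular Shell and Trident® X3® Polyethylene Insert studies".
- Section 2.1.2: "Usage of bone screw fixation will be recorded and compared between the" Tritanium shell group and the Trident HA Hemispherical Shell group.
- Section 9.1.2 lists the parameter only as "The usage of screw fixation".
- Section 9.1.5: "For comparison of usage of bone screw fixation between the Tritanium® Primary Acetabular Shell Study" and the Trident X3 study, a chi-square or Fisher's exact test at two-sided 0.05.

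**Shells.** Section 6.1 permits both the solid-back (catalog prefix 500-03) and the cluster-hole (502-03) shell. Section 1.4 adds: "This study is the first prospective data collection on both versions of the device". The product labeling says the company's 6.5 mm bone screws "can be used with the dome screw holes of the acetabular shells". The control shell is named only as the Trident HA Hemispherical Shell, with no hole pattern given.

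**Analysis set.** Section 9.4.4.1 bases all secondary efficacy analyses on the per protocol population, which leaves out censored cases and cases that cannot be evaluated at 5 years. Section 7.2 and the Surgical Details form in Appendix E show that screw use is captured at surgery.

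**The concern.** The two wordings define different quantities. One is the proportion of holed shells in which the surgeon used a screw. The other is the proportion of all shells with a screw, which is the first quantity multiplied by the share of shells that have holes. The same cases can give different answers under the two, and nothing in the plan says which wording governs the test.

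The all-shell comparison reflects screw use in holed shells only if the solid-back share is similar in the study and the control. Neither share is given. Section 9.1.5 provides for adjustment when baseline variables differ, with age, gender and diagnosis as examples, but does not name shell version. If the definition stays open, it could be settled after both results are known.

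Separately, a case lost before 5 years still has a known screw outcome, so the 5-year availability rule discards data for no gain on this endpoint.

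**Working it through.** The plan states no sample size, rate or margin for screw usage, so there is no figure of its own to reproduce here. The 142 and 177 in Section 9.4.2 concern the primary endpoint and are unaffected.

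**Inputs from the documents**
- 240 implanted cases (Section 3.3).
- 20% lost by 5 years (Section 9.4.2), giving 240 × 0.8 = 192 in the per protocol set.
- Two-sided alpha 0.05, chi-square test (Section 9.1.5).

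**Assumptions (not in the documents)**
- u = screw use in holed shells, 40% in both studies, so there is no true difference.
- Control size 200.
- s1, s2 = solid-back share in the study and the control.
- Solid-back shells take no screws. This is inferred from the name and the labeling.

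**Model.** All-shell rates are u(1 − s1) and u(1 − s2). The probability of a significant result comes from exact enumeration of two independent binomials, with the pooled z test (chi-square without continuity correction) and no covariate adjustment.

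**1. All-holed control (s2 = 0), study share varied, 192 v 200**

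| s1 | Study rate | Control rate | P(significantly lower) |
|---|---|---|---|
| 2% | 0.40 × 0.98 = 39.2% | 40% | 0.036 |
| 5% | 0.40 × 0.95 = 38.0% | 40% | 0.060 |
| 10% | 0.40 × 0.90 = 36.0% | 40% | 0.126 |
| 30% | 0.40 × 0.70 = 28.0% | 40% | 0.711 |

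The reference value is about 0.025 in each direction. At a small share the distortion is slight.

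**2. Study share fixed at 30%, control share varied, 192 v 200**

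| s2 | Control rate | P(lower) | P(higher) |
|---|---|---|---|
| 0% | 40% | 0.711 | <0.001 |
| 10% | 36% | 0.398 | <0.001 |
| 20% | 32% | 0.137 | 0.002 |
| 30% | 28% | 0.025 | 0.025 |
| 40% | 24% | 0.002 | 0.146 |
| 50% | 20% | <0.001 | 0.462 |

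Equal shares remove the problem, and a larger control share reverses its direction.

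**3. Cluster-hole test, no selection.** With 40% use in holed shells in both studies, all 240 cases counted and s1 = 30%, there are 240 × 0.7 = 168 cluster-hole cases. Against 200, 140 or 100 holed controls, the probability of a significant result stays near nominal in each direction (0.022 to 0.027 over 10% to 60% use).

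**4. Cluster-hole test, with selection.** Suppose overall use is 28% in both studies, the control is all-holed, and the study's 30% solid-back cases are those judged to need no screw. Use among cluster-hole cases is then 0.28 / 0.70 = 40%, against 28% in the control. The all-shell test (240 v 200) is significant 2.5% of the time in each direction. The cluster-hole test (168 v 200) is significantly higher with probability 0.68, or 0.63 on a loss-adjusted 134 (192 × 0.7).

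**5. Analysis set.** 240 − 192 = 48 known values dropped. At 40% use the 95% CI half-width is 1.96 × √(0.4 × 0.6 / n): 6.2 points at n = 240 and 6.9 at n = 192, a ratio of √(240/192) = 1.118.

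**The case against.** The texts can be read together. The synopsis objective names the population, and the later lines are short statements of endpoint and test. No section says that solid-back cases enter the screw comparison. Leaving out a qualifier is weaker than contradicting it. This stands in part: one clarifying phrase would settle the matter. But Section 2.1.2 is itself an objective and is worded for the whole shell group, and the limit is already missing from the test within the same synopsis.

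The 71% figure depends on a 30% solid-back share for which the documents offer no basis. At 10% the figure is 13%, and at 2% it is 4%. This stands, and it is why the range is shown.

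Cluster-hole cases are not a neutral subset. If surgeons choose solid-back when they expect no screw, restricting to cluster-hole cases conditions on that judgment, and step 4 shows the restricted test can then mislead while the all-shell test does not. This also stands. The reason to test the cluster-hole population is that it is the only restricted population the plan states as its objective. It has not been shown to be less prone to bias in every case.

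Finally, analyzing every implanted case without qualification would readmit cases that Section 9.4.4.4 removes for deviations that could affect outcome. The fix therefore leaves that rule in place.

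**Conclusion.** The planned test does not match the synopsis objective, and the plan does not say which governs. The all-shell test partly measures shell choice if the solid-back share differs between studies. That rests on the inference that solid-back shells do not take dome screws, which the documents suggest but do not state.

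The size and direction are unknown. Under the assumptions above (40% use in holed shells, 192 v 200, all-holed control), the probability of a spurious significantly lower result runs from about 4% to 71% as the study's solid-back share goes from 2% to 30%.

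Three stronger conclusions a reader might infer are not supported:
- That the comparison will understate Tritanium screw use. A control with the larger solid-back share would push the result the other way, and equal shares would leave it undistorted.
- That the cluster-hole test is always the safer one. The selection case shows otherwise.
- That the 5-year restriction biases the screw rate. The documents support only a minor loss of precision (half-width 6.2 to 6.9 points at 40% use). Any selection effect cannot be sized from them.

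The priority is low. The endpoint is secondary and has no bearing on the primary decision.

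**What to change.** - **Section 9.1.5**, with matching text in the synopsis methodology and Sections 2.1.2 and 9.1.2: test the proportion of implanted cluster-hole cases (catalog prefix 502-03) with at least one bone screw, against Trident X3 cases whose shells had screw holes.
- **Report alongside**, for each study, the all-shell rate and the solid-back share. State that shell choice may reflect anticipated need for screws, so a difference seen under only one definition is not read as a device effect.
- **If the control hole pattern cannot be obtained**, present the all-shell comparison as descriptive, with that limitation stated.
- **Section 9.4.4.1**: exempt screw usage from the 5-year availability requirement, and keep the censoring rule in Section 9.4.4.4.

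The cost is wording in the synopsis and four sections. This study needs no new data: the surgical form records the shell product and a Yes/No screw field, and the catalog prefix gives the version. The one outside task is a look-up of hole pattern in the Trident X3 data.
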